Effect of pre-operative tizanidine on postoperative urinary retention after sacrospinous vaginal vault suspension: a pilot study

Principal Investigator
[name] [name]

Co-PI
[name]

Clinical Research Supervisor
[name]

Sub-Investigator(s)
[name] MPH
[name]
[name]
[name]
[name]

Sponsor
None

Site of Investigation
Northshore University Health System

Date of Protocol: 6/4/2025

Protocol Version: 1

Purpose

The purpose of this study is to evaluate the effect of tizanidine on postoperative urinary retention after sacrospinous vaginal vault suspension compared with baseline data.

Background

Postoperative urinary retention has been defined as the inability to void despite having fluid in the bladder during the postoperative period (1). Urinary retention after pelvic reconstructive surgery requiring indwelling catheter or self-catheterization usage occurs in approximately 30-60% of patients postoperatively (1,2,3). Our prior retrospective chart review reviewing postoperative urinary retention rates after pelvic reconstructive surgery demonstrated postoperative urinary retention after a sacrospinous vaginal vault suspension to be approximately 78.9%.

Each patient after surgery undergoes a “voiding trial” where their voided volume is compared to their post-void residual volume. “Passing” a voiding trial has traditionally been defined as voiding a greater volume than the post-void residual volume (4). If the patient does not “pass” the voiding trial, the patient is characterized as having postoperative urinary retention and is discharged home with an indwelling catheter to prevent detrusor injury from bladder overdistention, pain and urinary tract infection (5).

Many women consider being discharged home with a Foley catheter to be a surgical complication and describe catheter use as the worst aspect of their surgery (1,6). Indwelling catheters are the leading cause of hospital-acquired urinary tract infections (UTIs), are often a source of embarrassment and inconvenience for patients, and often require additional office visits and healthcare utilization (7).

The leading hypotheses regarding the incidence of postoperative urinary retention after sacrospinous ligament suspension includes postoperative pain and pelvic floor muscle spasm leading to retention. The sacrospinous suspension includes a suture that is passed through the sacrospinous ligament and, therefore, through the coccygeus muscle with irritation of the pudendal nerve (8). The pelvic floor is a synergistic team of muscles that work together to support the pelvic organs and spasm of the coccygeus muscle, rather than an isolated muscle, can cause spasm of the entirety of the pelvic floor leading to retention. Tizanidine is a muscle relaxant which can work to alleviate this spasm and, theoretically, prevent postoperative urinary retention (9). Tizanidine also works as an alpha-adrenergic receptor blocker which can increase smooth muscle relaxation around the urethra specifically and, theoretically, improve urine flow (9).

Tizanidine is also frequently given for postoperative pain after sacrospinous ligament suspension and may act as an adjunct to a non-narcotic pain regimen to improve postoperative pain while reducing narcotic use after surgery. Postoperative buttock and posterior thigh pain are common symptoms after SSLF, with immediate pain reported in 6–84% of patients and persistent pain at 6 weeks occurring in 1–15% (7). Untreated acute postoperative pain has been shown to lead to increased morbidity and mortality (10). Pain is the most common reason for a postoperative unplanned hospital admission and poor postoperative pain control can lead to decreased ambulation, increased incidence of thromboembolism, and decreased inspiratory effort leading to postoperative pneumonia, therefore postoperative pain control is critical (11,12). In a country with rising narcotic-use and dependence, it is critical that we continue to explore non-narcotic alternatives for patients after surgery.

Postoperative urinary retention is extremely common after pelvic reconstructive surgery involving a sacrospinous vaginal vault suspension and is extremely bothersome to patients. Tizanidine is a low-risk,

well tolerated, cost-effective medication (9). No study to date has evaluated preoperative administration of tizanidine for postoperative urinary retention.

Hypothesis

We hypothesize that providing tizanidine preoperatively will improve postoperative urinary retention rates compared with our previously defined baseline data.

Objectives

The **primary objective** of this study is to evaluate whether preoperative administration of tizanidine will decrease the rate of postoperative urinary retention sacrospinous vaginal vault suspension compared with previously defined data. The **secondary objective** of this study is to evaluate for any differences in postoperative pain after administration of tizanidine compared to previously defined data.

Specific Aims

1. Evaluate the postoperative urinary retention rate in patients undergoing sacrospinous ligament suspension after postoperative administration of tizanidine.
2. Evaluate the postoperative pain scores after postoperative administration of tizanidine in patients undergoing sacrospinous vaginal vault suspension (postoperative nursing documentation performed in the recovery area based on a Likert scale of 0-10) and compare the differences in postoperative pain with previously collected data.
3. Evaluate the difference in unplanned admission the day of surgery or unplanned admission within 30 days after surgery, unplanned office visits within 30 days after surgery or Northshore encounters within 30 days after surgery after postoperative administration of tizanidine. These medical encounters will include any need for additional medical treatment, phone calls, complications or patient concerns within 30 days postoperatively. This data will be collected via chart review.

Outcome measures

1. Primary outcome measure:
 - a. Determine the postoperative urinary retention rates in patients undergoing a sacrospinous ligament suspension after postoperative administration of tizanidine. This will be determined immediately postoperative in the postoperative recovery room based on whether patients pass or fail their voiding trial described above. The result will be documented in electronic medical records and obtained from chart review.
2. Secondary outcome measures:
 - a. Determine differences in postoperative pain after postoperative administration of tizanidine. This data will be obtained by electronic data pull and chart review.
 - b. Determine the difference in unplanned admissions, office visits or Northshore encounters within 30 days after surgery after postoperative administration of tizanidine. This data will be collected via chart review.

Methods

This is a prospective trial of patients who are undergoing sacrospinous ligament suspension with or without concomitant incontinence or pelvic reconstructive surgery with the Center for Pelvic Health at the Northshore University Health System.

Women presenting to our tertiary urogynecology clinic with pelvic organ prolapse who decide to proceed with surgical treatment via a sacrospinous ligament suspension will be invited to participate in this study. This study will be discussed with the patient by their surgeon during their clinic initial screening visit or preoperative visit based on inclusion and exclusion criteria listed below. This study will involve no additional pre-operative tests or questionnaires, beyond our routine clinical pathway for women presenting with stress urinary incontinence. Written consent will be obtained.

During the initial clinic visit or at a subsequent encounter prior to their surgery, patients will be provided information on the research study by their care provider and given the opportunity to ask any questions. Patients will then be given a consent form to take home and review, discuss with others and consider participation. At the second preoperative encounter, patients will have another opportunity to discuss the study and ask any questions to their care provider. At that point, patients will be given the opportunity to sign the consent form if they would like to participate in the study. Participation is voluntary. For patients who will not have a second preoperative clinic visit prior to surgery, during the initial clinic visit, the care provider will discuss the research study, provide a consent form to the patient to review and ask for permission from the patient to be contacted by a study team member. If permission is granted, a study team member will contact the patient via telephone to discuss the study further and allow for the patient to consider participation in the study and ask any questions. If at that time the patient decides to participate in the study, written consent will be obtained the morning of surgery. All consent documentation and research participation will be documented in the patient's chart.

Patients who are undergoing a sacrospinous ligament suspension will be enrolled (after the previously described informed consent discussion) to receive a single preoperative dose of tizanidine 2mg or in the preoperative holding area on the day of their scheduled surgery as well as continued tizanidine postoperatively as needed every 6 hours.

After surgery, patients will then undergo a voiding trial in the recovery area. As described in prior studies, the patient will fail the voiding trial if voided volume is less than the PVR volume. Upon failing the voiding trial, the patient will be discharged home with a Foley catheter with plan for outpatient Foley catheter removal, consistent with our current protocol. According to our current protocol, patients discharged with a Foley catheter can either remove the catheter at home in 48-72 hours after surgery or call our office to have it removed at the next available appointment within 2-5 days postoperatively.

We will then evaluate the rate of postoperative urinary retention after administration of tizanidine compared with our previously studied and documented postoperative urinary retention incidence after sacrospinous ligament. Any collected information will be de-identified.

The current rate of postoperative urinary retention at our institution based on chart review after sacrospinous ligament suspension is 78.9%. Based on a sample size calculation to achieve 80% power, to evaluate for a 50% decrease in our urinary retention rate (from 78.9% to approximately 39.5%) we will need 23 subjects total. We aim to complete 23 subjects and expect to enroll 30 subjects to account for participant dropout.

Postoperative pain data will be evaluated by reviewing postoperative pain scales documented by the nursing staff in the postoperative area on a Likert scale 0-10. We will also evaluate narcotic administration in the postoperative area as a proxy for pain.

Inclusion criteria

Sacrospinous ligament suspension (CPT 57282)

Exclusion criteria

Age <18

Planned combined cases with colorectal surgery, general surgery, or gynecology-oncology

Known history of urinary retention

Known contraindication to tizanidine

Concomitant use of the following:

- Fluvoxamine, Ciprofloxacin (Patients are eligible if 3-5 half-lives have passed since they have taken Fluvoxamine, Ciprofloxacin)
- Potent CYP1A2 inhibitors
- Oral contraceptive
- Alpha-adrenergic agonists

Stage 4 Chronic Kidney Disease (eGFR <30), or worse

Breastfeeding

Hypersensitivity to tizanidine

Pre-existing psychiatric illness

Hypotension and chronic hypotension (<90/50 mmHg)

Variables

MRN

Age (at time of surgery)

Gravity and para

Race/ethnicity

Smoking status

Menopausal status

BMI

Comorbid conditions

Diabetes

Hypertension

Other cardiovascular disease

Respiratory disease

Obstructive sleep apnea

Chronic pain conditions

Prior hysterectomy

Prior abdominal surgery

History of prior prolapse surgery

History of prior incontinence surgery

Continence status

Prolapse stage

Location of surgery (Highland Park Hospital, Evanston)

Type of anesthesia

ASA grade

Incontinence procedure

Mid-urethral sling placement: CPT 57228

Concomitant prolapse procedures

Anterior colporrhaphy: CPT 57240

Posterior colporrhaphy: CPT 57250
Combined anterior and posterior colporrhaphy: CPT 57265
Hysterectomy
Rectopexy
Intraoperative complications
Additional procedures (ie. lysis of adhesions)
Intraoperative consultations
Length of procedure
Estimated blood loss
Surgeon
Surgeon experience (< 5 years, > 5 years)
Total time in PACU
Time of day in ASU
Total time in ASU
Immediate postoperative complications
Uncontrolled pain
Postoperative pain scores upon admission to the ASU
Postoperative pain scores at discharge
Reason for postoperative admission (surgeon choice, comorbid conditions, nausea/vomiting, etc.)
Time from voiding trial to void
Postoperative urinary retention
Postoperative urinary tract infection (UTI)
Unanticipated healthcare encounters
Urogynecology office visit (excluding voiding trial(s))
ED visit
Readmission within 30 days of discharge
Unplanned phone calls
Complications 30 days after discharge
Urinary tract infection
Reoperation
Venous thrombotic event

Statistical Methodology

A statistician from the NorthShore Research Institute will assist with statistical analysis. Data will be analyzed using SAS 9.4 (SAS Inc., Cary, NC). Demographic and clinical characteristics between groups will be compared using Student t-test (parametric) or Mann-Whitney U test (nonparametric) for continuous variables and Chi-squared test or Fisher exact test for categorical variables. Multivariable logistic regression models will be constructed to examine the relationship of an outcome with demographic and clinical covariates. Statistical significance will be defined at p-value < 0.05.

Literature review

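### The historical retention and pain data are not shown to be tizanidine-free, so it is unclear what the comparison estimates and the effect may be diluted

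*Combined protocol and SAP*

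**What the plan says.** The Background gives pain relief as an existing use of the study drug after the study operation: "Tizanidine is also frequently given for postoperative pain after sacrospinous ligament suspension". It gives no site, period, frequency or timing.

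There is no concurrent control. The Hypothesis reads "We hypothesize that providing tizanidine preoperatively will improve postoperative urinary retention rates compared with our previously defined baseline data". The Methods say "We will then evaluate the rate of postoperative urinary retention after administration of tizanidine compared with our previously studied and documented postoperative urinary retention incidence", and the secondary objective is to "evaluate for any differences in postoperative pain after administration of tizanidine compared to previously defined data". The baseline comes from an institutional chart review (Background: "Our prior retrospective chart review reviewing postoperative urinary retention rates after pelvic reconstructive surgery demonstrated postoperative urinary retention"). The Methods put its rate after this operation at 78.9%.

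Trial patients receive a preoperative dose and then as-needed tizanidine after surgery (Methods). Retention is judged by a voiding trial in the recovery area. Pain is scored there too, and the Variables list has scores on arrival in the ASU and at discharge.

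The Purpose speaks of the effect of tizanidine without qualification. The Hypothesis and primary objective specify the preoperative dose. No section describes tizanidine exposure in the historical patients, and neither the Variables list nor Statistical Methodology mentions it.

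**The concern.** A comparison with past patients shows the effect of a drug versus none only if those patients did not have the drug. The protocol's own account of usual practice leaves that open. If earlier patients had as-needed tizanidine, the two cohorts share part of the intervention, and the comparison is the planned regimen versus usual care.

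For retention, only doses given before the voiding trial matter. Pain is more exposed, because pain is the stated reason for existing use and scoring continues to discharge. With exposure unrecorded, a null pain result could mean that tizanidine does nothing or that both cohorts were treated, and the planned data could not tell these apart.

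**Working it through.** **Inputs.** Baseline retention 78.9%, planned halving to about 39.5%, 80% power and 23 completed subjects (Methods); p < 0.05 (Statistical Methodology). The share *f* of historical patients given tizanidine before the voiding trial is in no section, so it is an assumption shown over a range.

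**The plan's own figures.** 0.789 × 0.5 = 0.3945, as stated. For two groups, two-sided 0.05, pooled variance:

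n = [1.96·√(2 × 0.592 × 0.408) + 0.8416·√(0.789 × 0.211 + 0.395 × 0.605)]² / (0.789 − 0.395)² = (1.362 + 0.536)² / 0.1552 = 23.2 per group.

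The two-sided arcsine formula gives 23 per group. The stated 23 is thus reproduced as the size of one of two groups, the historical cohort being the other. Power with 23 per group is 80%.

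**Dilution, full effect at any time of dosing.** Let u be the drug-free rate and let the drug halve it whenever given.

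- The baseline is a mixture: 0.789 = u(1 − f) + 0.5·u·f, so u = 0.789 / (1 − f/2).
- Expected trial rate = u/2.
- Apparent relative reduction = 1 − 0.5 / (1 − f/2).

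| f | Drug-free rate | Trial rate | Apparent reduction | Power, 23 per group | Exact one-sample power, n = 23, one-sided 0.025 |
|---|---|---|---|---|---|
| 0 | 78.9% | 39.5% | 50% | 80% | 97% |
| 10% | 83.1% | 41.5% | 47% | 75% | 95% |
| 20% | 87.7% | 43.8% | 44% | 70% | 92% |
| 25% | 90.2% | 45.1% | 43% | 67% | 90% |
| 40% | 98.6% | 49.3% | 37.5% | 56% | 82% |

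The last column treats 78.9% as a fixed reference value. Under this assumption u reaches 100% at f = 2 × (1 − 0.789) = 42%, so the table stops at 40%.

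**Dilution, half effect in exposed historical patients.** Then u = 0.789 / (1 − f/4). At f = 25%, 50% and 75% the apparent reduction is 47%, 43% and 38%, with two-group power of 74%, 67% and 58%. No impossible rate arises in this range.

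**Pain.** The protocol gives no historical pain values, so no figure can be computed. The direction is the same if tizanidine lowers pain: exposed historical patients make the cohorts more alike.

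**The case against.** - **The Background sentence is general.** Elsewhere the protocol marks its own practice explicitly, as in "Our prior retrospective chart review reviewing postoperative urinary retention rates after pelvic reconstructive surgery demonstrated postoperative urinary retention". The sentence could describe use elsewhere, after the voiding trial or after discharge. This stands. A reader might infer that the historical patients probably had the drug, but the documents support only that they are not shown to be free of it.
- **The hypothesis concerns the preoperative dose.** If earlier patients had as-needed postoperative tizanidine, the contrast moves closer to that hypothesis. This stands for the primary objective. It does not cover the Purpose or the secondary objective, which read as drug versus no drug. A reader might infer that the comparison cannot show any effect of tizanidine, and that goes too far.
- **The planned 50% is relative to the observed baseline**, whatever its drug mix: "to evaluate for a 50% decrease in our urinary retention rate (from 78.9% to approximately 39.5"%). This stands. A reader might take the 42% limit as an internal contradiction in the plan. It is not: it arises only if the halving is read as drug versus none and as-needed doses work fully.
- **Dilution cannot create a false benefit.** This stands. A reader might infer that an observed difference could not be credited to tizanidine. On this ground alone that does not follow; other differences from historical patients are a separate matter.
- **The Variables list is not exhaustive.** The Methods plan to evaluate narcotic use, which is also absent from the list. The missing field is therefore weak evidence by itself, but no other section plans to collect tizanidine exposure either.

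**Conclusion.** The point holds as one of unclear contrast and possible dilution. The protocol reports frequent use of the study drug after the study operation, relies on historical data whose exposure it does not describe, and has no plan to find out.

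For retention, a true 50% reduction would appear as about 44% at 20% exposed and 37.5% at 40% exposed. Two-group power at 23 per group would fall from 80% to 70% and 56%. These figures assume that the drug halves retention and that exposed historical patients had the full effect before the voiding trial; a weaker effect in them means less dilution at the same f. Against a fixed 78.9%, power stays at about 82% even at 40% exposed, so interpretation suffers more than power.

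Pain is the outcome most affected, since its null result would be ambiguous. The bias from this source is towards no difference, and its actual size cannot be known until exposure is abstracted.

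**What to change.** 1. Abstract tizanidine use from the medication record for the historical cohort and the trial patients: yes or no, and time relative to the voiding trial and to each pain score. Add the item to Variables and report it for both cohorts.
2. State the whole-cohort comparison, the Purpose and the secondary objective as the planned tizanidine regimen versus usual care, which may include as-needed tizanidine. Reconcile this with the Specific Aims and Outcome measures, which refer to postoperative administration where the Hypothesis and primary objective say preoperative.
3. Add a sensitivity analysis against historical patients unexposed before the assessment concerned. It must stay secondary. Those patients probably had less pain, and because the Background names pain as a suspected cause of retention, they may also have had less retention.
4. If historical exposure cannot be recovered, limit the conclusion to the regimen versus usual care.

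The cost is one extra chart field in records the team has already reviewed, some protocol wording and a narrower claim. The unexposed subset will also be smaller than the full historical cohort if any of those patients were exposed.

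### The primary outcome is a charted pass/fail call compared with a historical rate of unstated rule, and the two volumes that decide the call are not on the Variables list

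*Combined protocol and SAP*

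**What the plan says.** Outcome measures, item 1a, sets the primary outcome as retention judged in the recovery room "based on whether patients pass or fail their voiding trial described above". On the source it says: "The result will be documented in electronic medical records and obtained from chart review".

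Two statements of the rule appear:

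- **Background.** Passing "has traditionally been defined as voiding a greater volume than the post-void residual volume". A patient who does not pass is dealt with in the next sentence: "the patient is characterized as having postoperative urinary retention and is discharged home with an indwelling catheter".
- **Methods.** "the patient will fail the voiding trial if voided volume is less than the PVR volume".

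The Background says that voided volume is compared with PVR for each patient. The Variables list has two items on the voiding trial: postoperative urinary retention, and "Time from voiding trial to void". It has no voided volume and no PVR.

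On design, Methods says that patients "will be enrolled (after the previously described informed consent discussion) to receive a single preoperative dose of tizanidine". Participation is documented in the patient's chart. No concurrent control, placebo, masked assessor or adjudication is described. The comparator is the institution's own rate of 78.9%, from a retrospective chart review (Background, Methods). The protocol does not say which rule that review used.

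**The concern.** The comparison is with an external historical rate, so any difference between periods in how pass and fail were called is indistinguishable from a drug effect. Three features leave room for such a difference. Staff who record the result can know that the patient had tizanidine. The rule behind the 78.9% is not given. The two measurements that would settle the matter are not among the items to be abstracted.

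A pass/fail result based on measured volumes is well protected against this, provided the volumes are kept and the same rule is applied to both cohorts. As listed, the dataset holds the call without the numbers behind it. With 23 patients, each changed classification moves the treated rate by 1/23 = 4.3 percentage points.

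**Working it through.** **1. The two rules side by side**

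| Volumes | Background | Methods |
|---|---|---|
| Voided > PVR | pass | not a fail |
| Voided < PVR | not a pass, so retention | fail |
| Voided = PVR | not a pass, so retention | not a fail |

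The rules agree except at exact equality, where they contradict each other. A patient who voids nothing and has a PVR above zero fails under both. Outcome measures refers back to the trial as described above it, and the only rule above it is the one in the Background. The Methods rule comes later.

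**2. Can the listed data show one rule in both cohorts?** Checking a call needs voided volume and PVR for each patient. Neither is listed for the treated cohort, and no volumes or rule are given for the historical one. So the listed dataset cannot show it. The source charts may hold the volumes; the protocol does not say.

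**3. Illustration of size**

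Inputs from the protocol: n = 23 and historical rate 0.789 (Methods); significance at p < 0.05, sidedness not stated (Statistical Methodology). No test is named for the primary comparison. Chi-squared and Fisher tests are named for comparing categorical characteristics between groups.

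The planned 23 reproduces as one group of a two-sample comparison. The arcsine difference is h = 2·arcsin√0.789 − 2·arcsin√0.395 = 0.828, and n = 2·((1.960 + 0.842)/0.828)² = 22.9, or 23 per group. A one-sample test against a fixed 78.9% needs fewer (normal approximation 8 to 12, exact binomial about 10 to 14). The intended test is therefore open, and three cut-offs are shown.

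Assumptions, not protocol figures: a share q of true failures in the treated cohort is charted as passes, with q = 5%, 10% or 15%; the historical cohort has the sizes shown in the cut-offs below, with its observed rate held at about 78.9%.

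Cut-offs for a significant decrease:

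- One-sample exact, one-sided 0.05: 14 or fewer retentions.
- One-sample exact, one-sided 0.025: 13 or fewer. Two-sided Fisher against 100 or 200 historical patients gives the same cut-off (p = 0.034 and 0.033 at 13; 0.103 and 0.065 at 14).
- Two-sided Fisher against 38 or 57 historical patients: 12 or fewer (p = 0.045 and 0.028 at 12; 0.085 and 0.055 at 13).

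With no drug effect, the probability of a significant decrease is P(X ≤ c), where X is binomial with n = 23 and p = 0.789 × (1 − q):

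| q | Charted rate | Patients affected (q × 23 × 0.789) | c = 14 | c = 13 | c = 12 |
|---|---|---|---|---|---|
| 0 | 78.9% | 0 | 3.8% | 1.3% | 0.4% |
| 5% | 75.0% | 0.9 | 9.7% | 4.1% | 1.5% |
| 10% | 71.0% | 1.8 | 19.7% | 9.9% | 4.3% |
| 15% | 67.1% | 2.7 | 33.3% | 19.5% | 9.9% |

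At each cut-off, a shift of one to three patients multiplies the false-positive probability several times. The absolute level depends heavily on the test.

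**The case against.** The strongest reply is that the outcome already rests on measured volumes and that nothing points to bias. That is fair. A reader might infer that recovery staff will be lenient with treated patients, but no part of the protocol shows this, or shows that the historical review used another rule. There is also a practical restraint: a failed trial leads to discharge with a catheter, so a false pass would send home without one a patient who had failed. Open-label conduct is itself an inference from the single-group design, and it is inherent in a pilot against baseline data.

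A reader might also take equal volumes to be unclassified, or treat the two rules as a main source of error. Neither is supported. The Background makes a tie retention and Methods does not fail it, so the tie is contradictory rather than undefined. It arises only at exact equality and would rarely change the result.

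A third tempting reading is that the outcome can never be verified. The gap is in the listed dataset; the volumes may be in the charts.

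Finally, collecting volumes blinds nobody, and bias in how the trial is conducted, such as its timing or repeat attempts, would affect the volumes too. This stands. The change addresses classification and recording, not conduct.

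What survives all of this is that the protocol neither states the historical rule nor lists the data that would show it to be the same.

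**Conclusion.** The point holds as an inexpensive improvement to outcome ascertainment. It is not evidence of a biased endpoint. A charted call, apparently open-label, is compared with a historical rate of unstated rule, and the listed data cannot confirm that the two cohorts were classified alike. The conflict at equality is minor, but the Background and Methods must be reconciled for the analysis definition.

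The false-positive figures are illustrations. They rest on assumed misclassification confined to the treated cohort, a true rate of 78.9% in both periods, and a test the plan does not specify. Across the three cut-offs, 5% to 15% misclassification gives between 1.5% and 33.3%, against 0.4% to 3.8% with none. The upper end should not be read as an expected error rate: it needs the largest assumed share together with the one-sample, one-sided 0.05 test.

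**What to change.** - Add voided volume and PVR at the first voiding trial in the recovery area to the Variables, for both cohorts.
- Define retention for analysis as one rule applied to those volumes, stating explicitly how a tie is assigned, and apply it identically to both cohorts. Reconcile the Background and Methods wording with it. This concerns the analysis definition only and leaves clinical management as it is.
- State which rule produced the historical 78.9%, and recompute that rate from volumes where they exist.
- Report the charted pass/fail as a sensitivity analysis. Where historical volumes are missing, use the charted result and report how many. Because that mixes two forms of ascertainment, also repeat the analysis with the charted call in both cohorts.

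The cost is two more numbers per chart. Some historical charts may lack them, in which case the volume-based comparison will be incomplete on that side and the repeat analysis matters more.
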